At the beginning of the procedure, after administration of nitroglycerin intracoronary (200 μ g), angiography will be performed with optimal visualization of epicardial coronary circulation and collateral blood flow to the area vascularized by the occluded artery. Angiographic quantification of collateral and collateral flow will be performed according to Rentrop and CC classifications

(16,30). Quantitative coronary angiography (QCA) will be used to quantify all coronary stenoses except CTO, which by definition is 100% stenosis.

Before the CTO recanalization, after adequate heparinization of the patient (by administration of 100 IU / kg heparin intravenously), the following functional parameters will be measured in each of the two non-occluded coronary arteries using a coronary wire with pressure and flow sensor (Combowire; Volcano Corp, San Diego, CA):

- Basal blood flow velocity

- Hyperemic blood flow velocity

- Coronary flow reserve (CFR)

- Mean blood pressure in the aorta (Pa) and at the sensor position (Pd)

- Fractional flow reserve (FFR)

- Hyperemic microvascular resistance (HMR)

Hyperemia will be caused by the administration of an intravenous infusion of adenosine ($140\mu g / kg / min$).

Following this, the CTO will be opened, using standard contemporary strategies and materials. After passage of the occlusion with the antegrade wire, a coronary wire with pressure and flow sensor will be introduced distally to the occlusion, and hyperemia will be induced by administering adenosine intravenously. After measuring the above functional parameters at this location, CTO dilatation and stent implantation will be initiated. Successful percutaneous coronary intervention (procedural success) is defined as the establishment of TIMI 3 flow with a residual stenosis of less than 30% after stent implantation or balloon dilatation. In the case of procedural success, the previously described functional parameters will be measured in the recovered coronary artery using the coronary wire with pressure and flow sensors when administered adenosine intravenously.

Finally, to evaluate the effect of CTO opening on the physiological parameters of the nonoccluded arteries, all the functional measurements mentioned above will be repeated with the same (or closest possible) sensor positions in both non-occluded arteries, as described in detail above.

C. Data collection in the procedure

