- Adverse cardiovascular events during the follow-up period - All patients will be monitored for adverse cardiovascular events during the follow-up period: cardiovascular death, non-fatal myocardial infarction, and any recurrent myocardial revascularisation.

SAMPLE SIZE

Based on the primary goal of the study, the required number of subjects was calculated according to the appropriate formula for Student's t-test for related samples using the following assumptions and data from previous published research: statistical power $(1-\beta) = 0.80$; statistical significance (α) = 0.05; expected change (increase) of coronary flow reserve (CFR) in the donor artery after opening of chronic total occlusion of 0.5 (41-43), expected standard deviation for invasive Doppler CFR in the reference artery of 0.85 (44).

$$n = \frac{(Z_{1-\frac{\alpha}{2}} + Z_{1-\beta})^2 \cdot \sigma^2}{\delta^2} = \frac{(1,960 + 0,842)^2 \cdot 0.85^2}{0,5^2} = 22,7 \approx 23$$

The sample size we calculated to be 23 patients, based on the above assumptions. Taking into account that the success of the procedure of opening a chronic total occlusion at the Cardiology Clinic of the Clinical Center of Serbia is 90% and that 15% of the respondents will be unavailable for a six-month follow-up, a total of 30 patients should be included.

STATYSTICAL ANALYSIS

- The following statistical methods will be used for data description:

Mean, median, standard deviation, interquartile range

- The following methods of analytical statistics will be used:

chi-square test, Student's t-test for independent and related samples, correlation, linear regression, logistic regression, The ROC curve and C-statistics will be used to determine the cut-off values. All tests will be realized as two-way. A p-value of <0.05 will be considered statistically significant. Data analysis will be done in the SPSS statistical software package (version 19 or above).

References:

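### The 23 required pairs come from a normal-quantile formula and give 76.9% power for the paired t-test, not 80% (25 are needed); the six-month loss does not belong in a calculation for in-procedure invasive CFR, for which 30 enrolled is enough

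*Combined protocol and SAP*

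**What the plan says.** The Sample Size section says the number was obtained "according to the appropriate formula for Student's t-test for related samples". Its inputs are power 0.80, alpha 0.05, an expected rise in donor-artery CFR of 0.5, and an SD of 0.85, which it describes as that of invasive Doppler CFR in the reference artery. The Statistical Analysis section adds: "All tests will be realized as two-way". The printed formula uses the normal quantiles 1.960 and 0.842 and gives 22.7. The text concludes: "The sample size we calculated to be 23 patients, based on the above assumptions".

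The enrolment figure then assumes 90% procedural success and that "15% of the respondents will be unavailable for a six-month follow-up, a total of 30 patients should be included".

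On timing, section B (data collection during PCI) takes the invasive measurements before the occlusion is opened. At the end of the same procedure, "all the functional measurements mentioned above will be repeated with the same (or closest possible) sensor positions in both non-occluded arteries". At six months, section C lists CFR by non-invasive Doppler echocardiography, with catheterization only where there is a clinical indication. The primary goal under Objectives gives neither a time point nor a measurement method.

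**The concern.** Two parts of the paragraph do not fit the analysis they are meant to support.

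First, the test named is a t-test but the formula is the one for a known SD. At about 20 pairs the difference is large enough to see: the SD has to be estimated, the critical value is larger, and the nominal 80% is not reached at 23 pairs.

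Second, the SD identifies the sized outcome as invasive CFR, and the invasive pair is complete when the procedure ends. A patient lost at six months has already supplied it. Deducting the 15% from that calculation misstates how many pairs the primary comparison will have.

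The stated power is the yardstick against which a null result for donor-artery CFR would be read. Both the number of pairs required and the number expected should therefore be right.

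**Working it through.** **Inputs** (Sample Size section unless noted): change δ = 0.5; SD σ = 0.85; α = 0.05, two-sided (Statistical Analysis section, and the quantile 1.960); target power 0.80; procedural success 0.90; six-month availability 1 − 0.15 = 0.85.

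**1. The plan's own figures.**

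n = (1.960 + 0.842)² × 0.85² / 0.5² = 7.851 × 0.7225 / 0.25 = 22.69, rounded up to 23. Reproduced.

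Enrolment: 23 / (0.90 × 0.85) = 23 / 0.765 = 30.07, stated as 30. Reproduced to within 0.07 of a patient.

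**2. Power of the named test.** For a two-sided paired t-test with n pairs, power is P(|T| > t₀.₉₇₅,ₙ₋₁), where T is noncentral t with n − 1 degrees of freedom and noncentrality (δ/σ)√n = 0.5882√n.

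| Pairs | Noncentrality | Critical t | Power, t-test | Power, normal approximation |
|---|---|---|---|---|
| 22 | 2.759 | 2.080 | 74.9% | 78.8% |
| 23 | 2.821 | 2.074 | 76.9% | 80.5% |
| 24 | 2.882 | 2.069 | 78.8% | 82.2% |
| 25 | 2.941 | 2.064 | 80.6% | 83.7% |
| 27 | 3.057 | 2.056 | 83.7% | 86.4% |

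The smallest n reaching 80% is 25. At 23 pairs the shortfall is 80 − 76.9 = 3.1 points.

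**3. What 30 enrolled delivers, under each reading of the attrition.**

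- Procedural failure only (invasive CFR, in the procedure): 30 × 0.90 = 27 expected pairs, power 83.7%. With a binomial number of successes, average power is 83.5% and the chance of at least 25 pairs is 93%. Enrolment needed for 25 pairs: 25 / 0.90 = 27.8, so 28.
- Both losses: 30 × 0.765 = 22.95 expected pairs, power 76.8%. With a binomial number of pairs, average power is 76.4% and the chance of at least 25 pairs is 26%. Enrolment needed for 25 pairs: 25 / 0.765 = 32.7, so 33.

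**4. Dependence on the SD.** Steps 1 to 3 use 0.85 as the SD of the before-after difference, as the plan's formula does. If 0.85 is instead the SD of a single CFR measurement, and the SDs before and after are equal, then SD of the difference = 0.85 × √(2(1 − ρ)). The correlation ρ is not in the documents, so the values below are assumptions.

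| Assumed ρ | SD of difference | Pairs needed for 80% | Power at 27 pairs |
|---|---|---|---|
| 0 | 1.202 | 48 | 55% |
| 0.3 | 1.006 | 34 | 70% |
| 0.5 | 0.850 | 25 | 84% |
| 0.7 | 0.658 | 16 | 97% |

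The two meanings of 0.85 coincide only at ρ = 0.5.

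**The case against.** The strongest defence is that the enrolment figure is sound. One total serves the whole study, which has six-month secondary goals (segmental kinetics) and six-month CFR, echocardiography and angina-questionnaire assessments. Carrying the six-month loss into total enrolment protects those analyses and is conservative for an outcome completed in the procedure. The formula and its quantiles are printed openly, the figure reproduces, and the z-for-t gap is two pairs, well below the uncertainty in the SD.

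Most of this stands. A reader might infer from the shortfall at 23 pairs that 30 enrolled is too few. The documents do not support that for invasive CFR measured in the procedure: 30 yields 27 expected pairs and more than 80% power. The two faults pull in opposite directions, and the second more than offsets the first. Nor is writing 30.07 as 30 worth pursuing.

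It is also tempting to quote 75–77% as the power of the six-month CFR comparison. That has no basis in the documents, because CFR is then measured non-invasively and 0.85 is given for the invasive measurement.

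What the defence does not rescue is the figure of 23. It is presented as the t-test requirement for 80% power, and it is not. The paragraph also never says that the 15% is there for the secondary analyses.

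**Conclusion.** The required number of pairs is wrong as written: 25, not 23, with 76.9% power at 23. The six-month loss is mismatched to the outcome that the SD describes. The enrolment of 30 is adequate on the in-procedure reading (27 pairs, about 84%) and falls to about 77% only if the primary comparison is subject to the six-month loss.

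This rests on four assumptions:

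- The primary comparison is invasive CFR within the procedure. The Sample Size section and section B imply this, but the Objectives do not state it.
- 0.85 is the SD of the within-patient change. The plan describes it otherwise, and power at 27 pairs runs from about 55% to 97% over the correlations shown. This matters far more than the two-pair correction.
- Every successful procedure yields a usable pair. The Measurement and Definition section limits the invasive parameters to subjects in whom they are technically feasible, and 27 is only two pairs above the 25 needed.
- A change of 0.5 is realistic at that time point. The Background reports a non-invasive rise of that size at three months (1.8 to 2.3) and no increase within 24 hours.

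This is a correction to stated figures, not a flaw in the design.

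**What to change.** Keep 30 enrolled and reword the Sample Size paragraph:

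1. Replace 23 with 25 pairs as the number the paired t-test needs for 80% power on the stated inputs.
2. Name in-procedure invasive donor-artery CFR as the outcome the calculation is for, and apply only the 10% procedural-failure allowance to it: 27 expected pairs and about 84% power, with fewer pairs if some measurements are not feasible.
3. Describe the 15% loss as an allowance for the six-month secondary analyses, and give no power figure for six-month non-invasive CFR.
4. State that these figures take 0.85 as the SD of the paired change. Give the range of power at 27 pairs, assuming equal SDs: about 55%, 70%, 84% and 97% at correlations of 0, 0.3, 0.5 and 0.7.

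The cost is a rewritten paragraph and a slightly less favourable stated requirement. No extra patients are needed and no procedure changes.

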
Previous studies have not sufficiently examined the relationship between collateral flow changes after PCI for CTO and changes in functional parameters of the donor artery with the amount of viable myocardium and segmental function of the left ventricle after revascularization. Also, the association of the phenomenon of coronary theft with the viability and occurrence of inducible myocardial ischemia has not been sufficiently investigated.

WORKING HYPOTHESIS

- 1. Following successful recanalization of chronic total coronary artery occlusion, the hemodynamic microcirculatory parameters (CFR, FFR, HMR) in the non-occluded (collateral donor) coronary artery will change as compared to the values before the procedure.
- 2. The magnitude of change in these parameters depends on the size of the collateral blood flow to the territory of the occluded coronary artery and the amount of viable myocardium in the vascularization zone of the occluded artery.

OBJECTIVES OF THE RESEARCH

- 1. The primary goal of the study is to determine the magnitude and direction of change in the functional parameters of microcirculation in collateral donor coronary artery after the successful opening of the chronic total occlusion.
- 2. The secondary goals of the study are:
- a) determination of the factors on which the change in hemodynamic parameters of the nonoccluded arteries depend,
- b) determining the factors that influence the improvement of segmental kinetics of the left ventricle after six months from the recanalization of the occluded artery,
- c) determination of correlation of functional parameters of microcirculation with ischemia, viability and segmental kinetics of the left ventricle,
- d) determining the correlation (change) of microcirculatory functional parameters with the quality of life determined by the Seattle Angina Questionnaire.

STUDY PROTOCOL

A. Data collection before intervention

In all patients, the following tests will be performed in the period before the intervention:

- Electrocardiogram,
- Echocardiographic examination,
- Stressechocardiographic test,
- Measurement of coronary flow reserve for collateral donor artery (RCA or LAD) by non-invasive transthoracic Doppler echocardiography,
- Scintigraphy (SPECT) for detection of viable myocardium in the CTO area,
- Seattle Angina Questionnaire

B. Data collection during PCI for CTO

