- The Seattle Angina Questionnaire is a modern and validated instrument for assessing the quality of life in patients with coronary disease (32). This questionnaire is based on five different domains that are assessed in patients: physical limitation, anginal stability, anginal frequency, treatment satisfaction and disease perception.

- Myocardial scintigraphy - All patients will have a 740 MBg 99mTc-MIBI myocardial scintigraphy given intravenously 10-15 minutes after sublingual administration of 0.5mg nitroglycerin (33) before attempting to recanalize the occlusion. The recording will take place 45-60 minutes after the administration of the radiopharmaceuticals, in a supine position, with a single gamma camera equipped with a high-resolution low energy collimator. 64 projections will be taken in the 180-degree range (starting from 45 degrees from the right front oblique to 45 degrees from the left rear position). After the reconstruction of the image, semi-quantification of myocardial perfusion and function will be done software. The size and severity of the perfusion defect will be calculated based on a 17-segment radiopharmaceutical uptake model and based on a guide from the European Nuclear Medicine Association and the European Association of Cardiologists for radionuclide imaging of cardiac function (34). The total download score of MIBI radiopharmaceuticals (SRS) will be calculated. The size and severity of the perfusion defect will also be indicated according to each of the three major vascular territories: anterior descendant, circumflex, and right coronary artery. Assessment of regional left ventricular wall thickness will be assessed by visual inspection in the Chinese mode of SPECT perfusion images (34). The presence of viable myocardium in the infarct zone will be considered as the absorption of radiopharmaceuticals \geq 55% of normal perfusion, with left-wall wall thickness gain (35–37). Also, the left ventricular ejection fraction, end-diastolic volume, and end-systolic volume will be evaluated using an automated algorithm (38).

- Echocardiography - Transthoracic echocardiographic examination will be performed in all subjects. All standard echocardiographic sections will be made. Measurements from orthogonal apical sections ("two and four cavities") will be used to estimate the global function of the left ventricle, with the simulation fraction calculated using the Simpson method. A 17-segment

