model will be used to calculate the wall motion score index of the left ventricular segment, while segmental kinetics will be constructed as follows: 1-normal segment kinetics, 2-hypokinesia, 3-akinesia, and 4- dyskinesia. This score will be calculated by dividing the sum of the mobility levels of the individual segments by the total number of visualized segments (39).

Stressechocardiographic test - a submaximal, symptom-limited stress-echocardiographic test on a Bruce protocol will be performed in all subjects. Before the test, at the end of each load step, and after the test is completed, arterial blood pressure and SF will be measured. The criteria for discontinuation of the test are: onset of anginal problems, fatigue, reaching submaximal frequency, the onset of ST depression greater than 1 mm, and the onset of hypertensive reaction (blood pressure greater than 240/130 mmHg). According to the protocol of the stressechocardiographic test, an echocardiographic examination in the left decubital position will be done to everyone before and immediately after the test. The test was defined as positive for the presence of inducible myocardial ischemia if there was a deterioration of left ventricular segmental kinetics at the EHO after the test.

- Measurement of coronary flow reserve for LAD artery - Transthoracic Doppler echocardiographic examination will record blood flow velocities in the LAD artery, at rest and after induction of hyperemia by administering adenosine intravenously (0.14 mg/kg/ min). Coronary flow reserve will be calculated as the ratio of maximum hyperemic and maximum basal flow rate (40).

- The following invasive functional parameters will be determined for all subjects where technically feasible:

- Basal blood flow velocity

- Hyperemic blood flow velocity
- Mean blood pressure in the aorta (Pa) and at the sensor position (Pd)
- Coronary flow reserve (CFR)
- Fractional flow reserve (FFR)
- Hyperemic microvascular resistance (HMR)

- Procedural complications - All patients will be monitored for the occurrence of periprocedural complications, including myocardial infarction, coronary perforation, cardiac tamponade, emergency cardiac surgery, complications at the site of vascular access.

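### ROC cut-offs would be chosen in 23 to 30 patients with no correction for optimism, so sensitivity and specificity reported at those cut-offs would be overstated

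*Combined protocol and SAP*

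**What the plan says.** The statistical analysis section lists its methods in a few lines. On thresholds it says only: "The ROC curve and C-statistics will be used to determine the cut-off values". It names no marker, outcome, direction, cut-off criterion, unit of analysis, confidence interval, resampling or validation sample.

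The sample size section sizes the study on the paired change in donor-artery CFR alone. It assumes 90% procedural success and that "15% of the respondents will be unavailable for a six-month follow-up, a total of 30 patients should be included".

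The secondary objectives suggest possible ROC targets but link none of them to ROC:

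- Objective 2b is "determining the factors that influence the improvement of segmental kinetics of the left ventricle after six months from the recanalization". The echocardiography definition gives a four-level segment score and an averaged index. No rule says how much change counts as improvement.
- Objective 2c relates the functional parameters to ischemia, viability and segmental kinetics. Two of these have yes/no rules under Measurement and Definition: a positive stress-echo test, and SPECT viability ("The presence of viable myocardium in the infarct zone will be considered as the absorption of radiopharmaceuticals" at or above 55% of normal, with wall thickening).

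More than one vessel is measured per patient. After the occlusion is opened, "all the functional measurements mentioned above will be repeated with the same (or closest possible) sensor positions in both non-occluded arteries". Echo and SPECT are each scored on 17 segments.

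**The concern.** A cut-off that maximises accuracy in a small sample fits that sample's noise as well as the signal. Sensitivity and specificity computed at that cut-off in the same patients are therefore biased upwards, and the cut-off would move appreciably in a new sample. With 23 to 30 patients both effects are large. A published threshold, for example a CFR value said to predict recovery, could be taken up by readers although it would perform much worse elsewhere.

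Because marker, outcome and direction are open, they could also be settled after the data are seen, which adds to the optimism.

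**Working it through.** **1. The plan's own figures.** (1.960 + 0.842)² × 0.85² / 0.5² = 22.7, rounded up to 23, as stated. 23 / (0.90 × 0.85) = 30.07, against the stated 30.

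**2. Patients available for ROC.**
- Pre-procedure data only: at most 30.
- After procedural success: 30 × 0.90 = 27.
- With six-month data: 27 × 0.85 = 22.95, about 23.

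**3. Assumptions (none is in the documents).** One observation per patient; a marker normally distributed with equal SD in both outcome groups; direction fixed in advance; cut-off at the maximum of J = sensitivity + specificity − 1 (Youden); 30% or 50% events; true AUC from 0.50 to 0.80.

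**4. Best attainable J.** The separation between groups is d = √2 × Φ⁻¹(AUC), and the best J is 2Φ(d/2) − 1.
- AUC 0.70: d = 1.414 × 0.524 = 0.742; J = 2 × 0.6446 − 1 = 0.289.
- AUC 0.80: d = 1.414 × 0.842 = 1.190; J = 2 × 0.724 − 1 = 0.448.

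**5. Apparent against true J.** Simulation with 10,000 runs per setting; cells show mean apparent J at 30% / 50% events.

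| True AUC | n = 23 | n = 27 | n = 30 | True J at chosen cut-off |
|---|---|---|---|---|
| 0.50 | 0.243 / 0.221 | 0.230 / 0.207 | 0.220 / 0.196 | 0 |
| 0.60 | 0.351 / 0.332 | 0.338 / 0.316 | 0.326 / 0.305 | 0.114–0.116 |
| 0.70 | 0.468 / 0.454 | 0.459 / 0.438 | 0.448 / 0.428 | 0.247–0.252 |
| 0.80 | 0.599 / 0.586 | 0.590 / 0.572 | 0.584 / 0.564 | 0.403–0.409 |

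Example (AUC 0.70, n = 27, 50% events): apparent sensitivity and specificity are 0.694 and 0.744, so J = 0.438. The true values are 0.604 and 0.648, so J = 0.252. Each is overstated by 9 to 10 percentage points.

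**6. Stability of the cut-off.** The central 95% of chosen cut-offs spans 2.21–2.46 within-group SDs at AUC 0.70 and 1.84–2.02 at AUC 0.80. At AUC 0.70 that is about three times the distance between the group means (2.21 / 0.742 = 3.0).

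**7. The C-statistic.** With one prespecified marker and fixed direction it is unbiased: the simulated mean is 0.699–0.702 at a true 0.70. It is imprecise: its central 95% runs from 0.45–0.91 (n = 23, 30% events) to 0.50–0.88 (n = 30, 50% events). If direction is picked from the data, a useless marker averages an apparent AUC of about 0.59–0.61. If the best of six independent useless markers is also picked, the average is 0.67–0.72.

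**8. What a bootstrap recovers.** 400 datasets × 200 stratified resamples, 40% events, one marker, fixed direction; cells show apparent / corrected / true J.

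| True AUC | n = 23 | n = 27 | n = 30 |
|---|---|---|---|
| 0.50 | 0.222 / 0.093 / 0 | 0.214 / 0.089 / 0 | 0.205 / 0.083 / 0 |
| 0.70 | 0.450 / 0.325 / 0.248 | 0.446 / 0.330 / 0.251 | 0.426 / 0.315 / 0.252 |
| 0.80 | 0.600 / 0.490 / 0.407 | 0.579 / 0.474 / 0.412 | 0.559 / 0.458 / 0.411 |

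Share of optimism removed = (apparent − corrected) / (apparent − true). At AUC 0.70, n = 23: 0.125 / 0.202 = 62%. Across settings it is about 57–69% (the rounded cells give 57–68%). The bootstrap 95% interval for the cut-off covered the optimal value in 93.5–95.5% of datasets at AUC 0.70 and in 90.5–93.2% at AUC 0.80.

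**The case against.** Several points on the other side stand.

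- **Same-patient evaluation is inferred.** A reader might take the plan to say that cut-offs will be judged where they were chosen. It does not say so, and it does not promise sensitivity or specificity. The inference rests on there being one cohort and no validation step.
- **Usable yes/no outcomes exist.** A reader might infer that ROC has no valid outcome here. Stress-echo ischemia and SPECT viability both have binary rules. What is missing is a link from either to ROC, and a rule for improvement under objective 2b.
- **The C-statistic is not inflated in every case.** It is unbiased for one prespecified marker with fixed direction. Nor can it be called safe in general: picking direction or marker from the data biases it, as does fitting a multivariable model, and logistic regression is on the methods list.
- **The magnitudes are illustrative.** AUC, prevalence, Youden criterion and one observation per patient are all assumed. Vessel- or segment-level analysis would behave differently.
- **The bootstrap is a partial remedy.** A useless marker keeps a corrected J of 0.08–0.09. Naming the analysis in advance and labelling the result exploratory do much of the work.

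It can also be said that such aims are exploratory anyway. The plan does not use that label for its cut-offs.

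**Conclusion.** The point holds in limited form. On the only cohort described, sensitivity and specificity reported at a ROC-derived cut-off would be overstated, and nothing in the plan corrects for it. Under the stated assumptions J is inflated by 0.20–0.24 for a useless marker, 0.18–0.22 at AUC 0.70 and about 0.16–0.20 at AUC 0.80, and the cut-off itself is poorly located. These are ranges under assumptions and do not predict this trial's results.

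The documents do not support a wider reading that the study's main result is compromised. The primary paired comparison and its sample size do not depend on ROC, and nothing in the protocol uses a derived cut-off for treatment or for the primary conclusion. The change should be made because it is cheap and protects the secondary findings.

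**What to change.** Replace the ROC sentence with text that commits, for every cut-off reported, to:

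1. Sensitivity and specificity corrected for optimism by a bootstrap that repeats the whole selection in each resample: the cut-off search and any choice of direction or marker. Resample patients, not vessels or segments.
2. A bootstrap interval for the cut-off and a confidence interval for the C-statistic, with optimism correction of the C-statistic where direction, marker or a multivariable model is chosen from the data.
3. The label 'exploratory, needs external validation'.

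To make this workable, state before analysis, for each ROC analysis: marker, outcome with its yes/no rule (for objective 2b, the wall-motion change that counts as improvement), direction, cut-off criterion, unit of analysis and patient set.

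The cost is SAP wording and a short bootstrap on data already planned; no patients or visits are added. Reported accuracy will be lower, and no ready-made threshold will result. Since about a third or more of the optimism remained in simulation, describe the values as partly corrected and keep the exploratory label. That simulation covered one marker with fixed direction, so it does not show how much optimism is removed when marker or direction is also selected.
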